9.2 Criteria for Determining Causal Relationship to the IMP

The criteria for determining the causal relationship of an AE with the IMP is presented in the table below.

Causal Relationship to the IMP	Criteria for Determining Causal Relationship
Definitely Related	There is clear evidence to suggest a causal relationship, and other possible contributing factors can be ruled out. The clinical event, including an abnormal laboratory test result, occurs in a plausible time relationship to placement of the IMP and cannot be explained by concurrent disease or other devices, drugs, or chemicals.
Possibly Related	There is some evidence to suggest a causal relationship (e.g., the event occurred within a reasonable time after the placement of the IMP). However, the influence of other factors may have contributed to the event (e.g., the subject's clinical condition, other concomitant events). Although an adverse effect may rate only as "possible" soon after discovery, it can be flagged as requiring more information and later be upgraded to probable or certain as appropriate.
Unlikely Related	A clinical event, including an abnormal laboratory test result, whose temporal relationship makes a causal relationship improbable (e.g., the event did not occur within a reasonable time after placement of the IMP) and in which other drugs or chemicals or underlying disease provide plausible explanations (e.g., the subject's clinical condition, other concomitant treatments).
Not Related	A clinical event, including an abnormal laboratory test result, which occurs when the subject was not exposed to the IMP or, another cause is obvious and in which there is sufficient information that the etiology of the event is not related to the IMP.

9.3 Criteria for Defining the Severity of an Adverse Event

Adverse events, including abnormal clinical laboratory values, will be assessed according to the criteria below and entered in the eCRF:

Grade	Severity Assessment Standard
1-Mild	Events require minimal or no treatment and do not interfere with the subject's daily activities.
2-Moderate	Events result in a low level of inconvenience or concern with the therapeutic measures. Moderate events may cause some interference with functioning.
3-Severe	Events interrupt a subject's usual daily activity and may require systemic drug therapy or other treatment. Severe events are usually incapacitating.
4-Life-threatening	Any adverse event that places the subject or participant, in the view of the investigator, at immediate risk of death from the reaction as it occurred, i.e., it does not include a reaction that, had it occurred in a more severe form, might have caused death.
5-Death	Death related to AE.

9.4 Reporting of Adverse Events

At each evaluation, the subject will be questioned in a general way and no specific symptoms will be suggested. If any AEs have occurred, they will be recorded on the AE pages of the eCRF and in the subject's medical record. If known, the diagnosis should be recorded in preference to the listing of individual signs and symptoms.

During the Screening period (Day -35 to Day 0 prior to implantation), only SAEs related to study procedures will be reported beginning at the time the subject signs the informed consent form. From Day 0 after implantation to 2 years post-implantation (Month 24 visit) or ET visit, whichever occurs earlier, all AEs will be reported.

During the long-term follow-up period from 2 years to 5 years post-implantation, only the following will be reported by the investigator:

- All SAEs considered related to the HAV
- All Events of Special Interest.

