4.2.2 Secondary Endpoints

4.2.2.1 Key Secondary Endpoints:

Efficacy

Time to loss of Primary Patency from implantation

- Defined as 'the interval from the time of access placement until any intervention designed to maintain or reestablish patency, access thrombosis or the measurement of patency', i.e., patent without interventions ([Sidawy 2002](#)).

Safety

Access-related infections ([CDC 2013](#))

4.2.2.2 Other Secondary Endpoints:

Efficacy

1. Rate of interventions required to achieve/maintain Secondary Patency
2. Time to loss of Primary Assisted Patency from implantation
 - a. Defined as 'the interval from the time of access placement until access thrombosis or the time of measurement of patency, including intervening manipulations (surgical or endovascular interventions) designed to maintain the functionality of patent access' i.e., patent without an intervention to clear a thrombus ([Sidawy 2002](#)).
3. Histopathological remodeling of any study conduit (based on any samples collected).
4. The efficiency of dialysis as assessed by $spKt/V_{urea}$ (obtained from dialysis unit for a subset of subjects).

Safety

1. Frequency and severity of AEs
2. Study conduit dilatation:
 - a. True aneurysm formation (conduit lumen diameter > 9 mm)
 - b. Pseudo-aneurysm formation
3. Study conduit spontaneous rupture
4. Anastomotic bleeding or spontaneous rupture

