4.2.3 Events of Special Interest

Events of Special Interest related to interventions and infections will be evaluated and include the following:

- Study conduit abandonment
- Thrombosis / thrombectomy
- Angioplasty or stenting
- Access-related infection

- Pseudo-aneurysm or true aneurysm (conduit lumen diameter >9 mm) formation
- Study conduit spontaneous rupture
 - Iatrogenic injuries are not an Event of Special Interest and should be reported as an AE
- Revision or ligation of the study conduit
- Study conduit removal
- Steal syndrome

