9.4.1 Reporting of Serious Adverse Events

Any SAE which occurs during the course of this study (as defined in [Section 9.1.1](#)), whether or not causally related to the IMP, must be reported by the investigator to CTI Safety immediately (**no later than 24 hours after learning of its occurrence**).

CTI Global Safety & Pharmacovigilance

SAE Telephone [contact]

SAE eFax #: Country-specific fax numbers will be provided in the study manual

E-mail: [contact]

If there are any questions, or if clarification is needed regarding the SAE, please contact the Medical Monitor in the respective region (see [Section 1](#)).

Follow-up information for the event should be sent promptly (within 7 days of the initial notification).

Full details of the SAE should be recorded on the medical records and in the eCRF.

The following minimum information is required:

- Study number,
- Subject number, gender and age,
- The date of report,
- A description of the SAE (event, seriousness of the event), and
- Causal relationship to the IMP.

Humacyte or Humacyte's designee will submit expedited safety reports to the regulatory agencies as necessary, and will inform the investigators of such regulatory reports. Investigators must submit safety reports as required by their IRB/IEC within timelines set by regional

regulations. Documentation of the submission to and receipt by the IRB/IEC of expedited safety reports should be retained by the site.

9.4.2 Monitoring and Reporting of Serious Adverse Events Not Related to the Implanted Conduit

Patients with ESRD have significant co-morbidities and typically experience many SAEs related to those co-morbidities that are not related to the implanted dialysis conduit. Investigators will be asked, as part of their reporting, to identify whether a particular SAE is study conduit-related.

For those events identified as not being related to the study conduit, Humacyte will monitor these events throughout the course of the study for any difference in frequency to confirm that there is not a link to the implanted conduit. Occurrences of non-conduit related SAEs will be excluded from expedited reporting to the applicable regulatory authorities and to IRB/IECs. If aggregate analysis of these events indicates they occur more frequently with the IMP, an expedited safety report may be submitted.

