Regardless of whether the SAE is considered study conduit related or not, the Principal Investigator's reporting obligations for events that meet the definition of a SAE as described in [Section 9.1.1](#) do not change.

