13.4 Safety Reporting

The Principal Investigator shall:

- Record every AE together with an assessment, in accordance with [Section 9](#) of this protocol
- Report to Humacyte, without unjustified delay, all SAEs and medically significant events as specified in [Section 9.1.1](#) of this protocol
- Supply Humacyte or designee, upon Humacyte's request, with any additional information related to the safety reporting of a particular event

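### After Month 24 the protocol gives two SAE reporting rules with no order of precedence, and the narrower rule names only the HAV

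*Protocol*

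**What the plan says.** Protocol 9.4 sets reporting by period. During Screening, only procedure-related SAEs are reported. From implantation to Month 24 or early termination, all adverse events are reported. From year 2 to year 5 only two categories remain: "All SAEs considered related to the HAV" and all Events of Special Interest. Appendix 1 footnote 10 repeats this restriction in the same terms.

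Section 9.4.1 says that "Any SAE which occurs during the course of this study" must be reported within 24 hours, whatever its causality. Section 13.4 lists among the investigator's duties: "Report to Humacyte, without unjustified delay, all SAEs and medically significant events as specified in" Section 9.1.1. Neither mentions Month 24.

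Section 9.4.2 asks investigators "to identify whether a particular SAE is study conduit-related". For those judged unrelated it says that "Humacyte will monitor these events throughout the course of the study for any difference in frequency". It closes by stating that the relatedness call does not alter the investigator's "reporting obligations for events that meet the definition of a SAE".

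Section 8.3.9 collects details of special-interest events to 5 years and requires any that are serious to be reported regardless of causality. Section 8.6.1.4 points back to it for the Month 30 to 60 visits.

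**The concern.** A site reading 9.4 or the visit-schedule footnote and a site reading 9.4.1 would report different events after Month 24. The narrower rule also names one arm's product only, although comparing the safety and tolerability of the two conduits is a stated secondary objective (Protocol 3.2.2). At stake is whether late serious events are collected on the same terms in both arms, and whether the sponsor can carry out the whole-study monitoring that 9.4.2 promises.

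**Working it through.** The plan states no figure on this point, so the check is of text. The passages side by side:

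| Protocol section | What is reported or monitored | Month 24 limit | Conduit named |
|---|---|---|---|
| 9.4; Appendix 1 footnote 10 | Related SAEs and special-interest events only | Yes, applies Months 24 to 60 | HAV |
| 9.4.1 | Any SAE, any causality | None | No restriction by conduit |
| 13.4 | All SAEs | None | No restriction by conduit |
| 9.4.2 | Sponsor monitors SAEs not related to the conduit | None | Study conduit, either arm |
| 8.3.9, reached from 8.6.1.4 | Special-interest events; serious ones regardless of causality | Runs to 5 years | Either arm |

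Applying each rule to a serious event after Month 24:

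| Type of event | 9.4, HAV subject | 9.4, ePTFE subject | 9.4.1, either arm |
|---|---|---|---|
| Special-interest event | Reported | Reported | Reported |
| Conduit-related, not on the list | Reported | Not reported | Reported |
| Not conduit-related, not on the list | Not reported | Not reported | Reported |

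The second row is the one-sided gap. The third row is the same in both arms, but it is what 9.4.2 needs for its monitoring. Under 9.4 alone, that monitoring would be limited after Month 24 to unrelated SAEs that are also special-interest events.

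**What falls in the second row.** Protocol 2.5.1 gives limb swelling and skin erosion as risks of both conduits, and 4.2.3 lists neither. Either would count here only if serious. Anastomotic bleeding is a less clean example. It is part of a named safety endpoint in 4.2.2.2 ("Anastomotic bleeding or spontaneous rupture") and is not listed in 4.2.3. However, that list opens with "Events of Special Interest related to interventions and infections will be evaluated and include the following", so it may not be exhaustive. Bleeding treated by revision, ligation or removal is already covered, and the SAP puts access bleeding under its special-interest heading.

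**How many subjects are in the window.** This bears on the cost of the fix and does not measure loss. After Month 24 only subjects with a patent conduit are followed (Protocol 4.3). Inputs: 175 per arm; 12-month secondary patency of 60% for ePTFE and 66% for HAV (Protocol 10.5); annual deaths of about 20% (SAP 6.1). Assumptions: constant hazards, deaths independent of abandonment, no transplant or withdrawal.

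- ePTFE at Month 24: 175 × 0.60² × 0.80² = 40.3
- HAV at Month 24: 175 × 0.66² × 0.80² = 48.8
- Both arms: 40.3 + 48.8 = 89.1

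If the withdrawn site's roughly 10% of subjects left before Month 24 and were spread evenly by arm (an assumption), ePTFE falls to 40.3 × 0.90 = 36.3. With a further 10% per year lost to transplant or withdrawal (also assumed, not in the documents), it is 36.3 × 0.90² = 29.4.

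The rate of off-list, ePTFE-related SAEs is not given, so no count of lost events follows from these figures.

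**The case against.** The best defense is that nothing conflicts. Section 9.4 is the parent section and sets what is reported in each period, while 9.4.1 sets the clock, the recipient and the content. The Screening rule in 9.4 fits this, since it too is narrower than any SAE and reads naturally as a scope for that period. Section 8.6 has no general adverse event item for Months 30 to 60, whereas 8.5.1.8 has one up to Month 24. This is a fair reading and may be what was meant. But 9.4.1 speaks of the whole study and of any causality, which goes beyond a clock, and 13.4 repeats the broad duty. The reading also leaves 9.4 favoring one arm's product, so the text needs correcting on either view.

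A reader might infer that 9.4.2 itself demands all SAEs. It does not: it preserves whatever duty exists elsewhere. Section 13.4 is a summary of duties that refers to Section 9 for recording and to 9.1.1 for the SAE definition. The main conflict is therefore between 9.4 with its footnote and 9.4.1.

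A reader might also infer that 9.4 makes the 9.4.2 monitoring impossible. It would be curtailed, because 8.3.9 keeps serious special-interest events reportable in both arms regardless of causality.

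**Conclusion.** The inconsistency stands and is worth correcting, but its weight is modest. Under 9.4.1 nothing is lost. Under 9.4, the one-sided part is confined to serious, conduit-related events off the special-interest list, in ePTFE subjects still patent after Month 24. Access-site problems are still documented in both arms under 8.6.1.4. The 18-month primary analysis, adverse event data to Month 24 and the access-infection comparison are unaffected. The remaining safety data are descriptive.

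Three stronger conclusions are tempting and not supported:

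- **The final safety tables will be biased.** SAP section 4 plans a final analysis after 60 months of follow-up, but no text says the SAE tables accumulate to that point. If they do, the gap would under-count ePTFE and so run against the HAV.
- **Late deaths will be missed.** Death is a censoring event, a disposition count (SAP 5.1) and a status summary (SAP 7.6), whatever the SAE rule.
- **Every ePTFE event must be rated unrelated.** Protocol 9.2 is worded against the IMP, which 2.1.1 defines as the HAV. But Protocol 9.1 and SAP 7.2 treat both arms as drugs for event reporting, and 9.4.2 asks about the study conduit. The intent is largely clear, so this is a minor clarification.

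Confidence is high on the conflict in the text and low on how many events it could affect.

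**What to change.** Reconcile Protocol 9.4 and Appendix 1 footnote 10 with 9.4.1, 9.4.2 and 13.4, so that one SAE rule applies after Month 24 on the same terms in both arms. If a relatedness restriction is kept, word it as related to the study conduit (HAV or ePTFE), and bring the 9.4.2 monitoring statement and the all-SAE wording of 9.4.1 and 13.4 into line with it. If the all-SAE rule is kept, remove the restriction from 9.4 and the footnote. The choice is the sponsor's.

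As a minor addition, state in 9.2 and beside the SAP relatedness tables that relatedness is judged against the implanted study conduit in both arms.

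The cost is protocol and SAP wording plus some late reporting. With a conduit-neutral restriction, the extra reporting falls on about 29 to 40 ePTFE subjects under the assumptions above, all already attending the same visits. With the all-SAE rule it covers both arms, about 89 subjects before site loss, transplant or withdrawal.

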9.4.1 Reporting of Serious Adverse Events

Any SAE which occurs during the course of this study (as defined in [Section 9.1.1](#)), whether or not causally related to the IMP, must be reported by the investigator to CTI Safety immediately (**no later than 24 hours after learning of its occurrence**).

CTI Global Safety & Pharmacovigilance

SAE Telephone [contact]

SAE eFax #: Country-specific fax numbers will be provided in the study manual

E-mail: [contact]

If there are any questions, or if clarification is needed regarding the SAE, please contact the Medical Monitor in the respective region (see [Section 1](#)).

Follow-up information for the event should be sent promptly (within 7 days of the initial notification).

Full details of the SAE should be recorded on the medical records and in the eCRF.

The following minimum information is required:

- Study number,
- Subject number, gender and age,
- The date of report,
- A description of the SAE (event, seriousness of the event), and
- Causal relationship to the IMP.

Humacyte or Humacyte's designee will submit expedited safety reports to the regulatory agencies as necessary, and will inform the investigators of such regulatory reports. Investigators must submit safety reports as required by their IRB/IEC within timelines set by regional

regulations. Documentation of the submission to and receipt by the IRB/IEC of expedited safety reports should be retained by the site.

9.4.2 Monitoring and Reporting of Serious Adverse Events Not Related to the Implanted Conduit

Patients with ESRD have significant co-morbidities and typically experience many SAEs related to those co-morbidities that are not related to the implanted dialysis conduit. Investigators will be asked, as part of their reporting, to identify whether a particular SAE is study conduit-related.

For those events identified as not being related to the study conduit, Humacyte will monitor these events throughout the course of the study for any difference in frequency to confirm that there is not a link to the implanted conduit. Occurrences of non-conduit related SAEs will be excluded from expedited reporting to the applicable regulatory authorities and to IRB/IECs. If aggregate analysis of these events indicates they occur more frequently with the IMP, an expedited safety report may be submitted.

Regardless of whether the SAE is considered study conduit related or not, the Principal Investigator's reporting obligations for events that meet the definition of a SAE as described in [Section 9.1.1](#) do not change.

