Figure 3	Images of Mid-Vessel Segment Explanted at 11-Months Post-Implant	35

List of Abbreviations

ADR	Adverse drug reaction
AE	Adverse event
ALT	Alanine transaminase
AST	Aspartate transaminase
AV	Arteriovenous
AVF	Autologous arteriovenous fistula
BUN	Blood urea nitrogen
CDC	Center for Disease Control and Prevention
CEC	Clinical Events Committee
CKD	Chronic kidney disease
CRO	Contract research organization
CVC	Central venous catheter
D	Day
DHHS	Department of Health and Human Services
DMC	Data Monitoring Committee
DTH	Delayed-type Hypersensitivity
ECG	Electrocardiogram
ECM	Extracellular Matrix
eCRF	Electronic case report form
ePTFE	Expanded polytetrafluoroethylene
ESA	Erythropoiesis-stimulating agent
ESRD	End-stage renal disease
ET	Early termination
GCP	Good Clinical Practice
GLP	Good Laboratory Practice
HAV	Human acellular vessel (note was HAVG [Human Acellular Vascular Graft])
HbA1c	Hemoglobin A1c
ICH	International Conference on Harmonization
ICMJE	International Committee of Medical Journal Editors
IEC	Independent ethics committee
IgG	Immunoglobulin G
IMP	Investigational medicinal product

List of Abbreviations

IMPD	Investigational medicinal product dossier
IND	Investigational new drug
INR	International normalized ratio
IRB	Institutional Review Board
ISO	International Organization for Standardization
ITT	Intent-to-Treat
LMWH	Low molecular weight heparin
M	Month
MedDRA	Medical Dictionary for Regulatory Activities
mlITT	Modified Intent-to-Treat
PAD	Peripheral arterial disease
PE	Physical examination
PHI	Protected health information
PP	Per Protocol
PRA	Panel reactive antibody
PT	Prothrombin time
PTFE	Polytetrafluoroethylene
RBC	Red blood cell
RRT	Renal replacement therapy
SAE	Serious adverse event
SOP	Standard operating procedure
spKt/V _{urea}	Measure of dialysis adequacy for a single hemodialysis treatment using the single pooled method
SUSAR	Suspected unexpected serious adverse reaction
ULN	Upper limit of normal
US	United States
WBC	White blood cell

Protocol Summary

Full Title	An Assessment of Humacyte's Human Acellular Vessel in Patients Needing Renal Replacement Therapy: A Comparison with ePTFE Grafts as Conduits for Hemodialysis (HUMANITY)
Clinical Trial Phase	Phase 3
Sponsor	Humacyte, Inc.
Planned Study Sites	Approximately 35 Sites in the US, Europe and Israel
Sample Size	At least 350 evaluable subjects with implanted study conduits; 175 with Human Acellular Vessel (HAV), 175 with an expanded polytetrafluoroethylene (ePTFE) graft

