10.4 Safety Analysis

The safety analysis will be conducted in the safety population.

For each of the two treatment groups, the access-related infection rate will be computed in 2 ways:

- Rate of access-related infections per 100 person-years of HAV/ePTFE use (i.e., censored at abandonment)
- Rate of access-related infections per 100 person-years over the 2-year post-implantation follow-up period

These analyses will be based on adjudicated events using a standardized definition of access-related infections ([CDC 2013](#)).

For each of the 2 definitions, the infection rates in the two arms will be compared using a Poisson regression model with treatment group and the randomization stratification variable as factors. This analysis will be conducted using a two-sided test at the alpha=0.05 level of significance.

All other safety data will be described only (i.e., no inferential statistics).

For the analysis of study conduit dilatation and aneurysm formation, descriptive data will be presented by Visit. In addition, the number of study conduits showing true aneurysm formation (internal conduit diameter >9 mm) or pseudo-aneurysm will be reported.

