Unless otherwise specified, continuous variables will be summarized by presenting the number of non-missing observations, mean, standard deviation, median, inter-quartile range, minimum and maximum. Categorical variables will be summarized by presenting the number of subjects and percentage for each category.

Unless otherwise noted, all tests of treatment effects will be conducted at a 2-sided alpha level of 0.05 and two-sided 95% confidence intervals (CI) will be calculated. All tests of interactions between treatment groups and other factors will be conducted at a 2-sided alpha level of 0.10, unless otherwise noted. Parametric and nonparametric methods, as determined by the distribution of each variable, will be used to test statistical hypotheses of continuous variables. In the event of highly skewed data, a logarithmic transformation will be considered prior to any statistical testing.

All p-values will be rounded to 3 decimal places. A p-value rounded to 1.000 will be displayed as >0.999, and a p-value rounded to 0.000 will be displayed as <0.001.

Multiplicity will be managed by testing the primary and key secondary endpoints in a hierarchical fashion. All analyses will be performed using data pooled across sites.

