## 6 EFFICACY ANALYSIS

### 6.1 PRIMARY EFFICACY ENDPOINT AND ANALYSIS

The primary efficacy endpoint is the time to loss of Secondary Patency assessed when all patients are at least 18 months after implantation (or have been censored). The primary analysis will be non-inferiority analysis using the following censoring rules:

- Subjects who have patent study conduits at the time of death, kidney transplant, voluntary withdrawal will be censored at that timepoint
- Subjects who are lost to follow-up will be censored at their last visit when it was known that the study conduit was patent
- Subjects who are lost to follow up and whose study conduit was not patent at the last completed visit will be treated as abandoned at the time of study conduit occlusion
- Subjects in whom a delayed decision is made to abandon the study conduit (e.g. delayed and then failed thrombectomy) will have the date of abandonment set as the date of the initial recognition of the thrombosis, not the date that a final decision is made
- For subjects who discontinue early or who complete without meeting criteria for the event, the time-to-event will be censored and defined as the number of days from randomization to the subject's last visit during the study

These censoring rules will apply to all 'time to' analyses. Subjects with End Stage Renal Disease (ESRD) have significant co-morbidities, with an annual death rate of ~20% (USRDS). Given the nature of the investigational product and the clinical setting, it is unlikely that the investigational product will be a causative factor in the overall death rate, and it is likely that the non-product related death rate will be similar in the two arms. For this reason, the primary analysis of Primary and Secondary Patency will censor deaths. However, a secondary analysis will be conducted in

which death is included as an event in the patency survival curves, to provide re-assurance that death does not modify the outcome of the trial.

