### **Adverse Events Summaries**

An overall summary of all TEAEs will be presented overall and by treatment group and will include the following:

- the number and percentage of subjects experiencing a TEAE
- the number and percentage of subjects experiencing a TEAE by strongest relationship to IMP assessed by Principal Investigator and sponsor
- the number and percentage of subjects experiencing a TEAE by strongest relationship to study procedure(s) assessed by Principal Investigator and sponsor
- the number and percentage of subjects experiencing a TEAE by greatest intensity (see Section 9.3 of study protocol for details on intensity)
- the number and percentage of subjects experiencing a TEAE leading to IMP abandonment
- the number and percentage of subjects experiencing a treatment emergent SAE (TESAE)
- Deaths

In the overall summary of TEAEs table, besides tabulating the number and percentage of subjects, the total number of TEAE episodes will also be provided. If a subject has repeated episodes of a particular TEAE, all episodes will be counted in the summary table.

In addition to an overall summary, the following safety data with no inferential statistics will be provided:

- All Treatment Emergent AEs by SOC and PT
- All Serious AEs by SOC and PT
- All Treatment Emergent AEs leading to outcome of death by SOC and PT
- All Treatment Emergent AEs by SOC, PT and greatest severity
- All Treatment Emergent AEs by SOC, PT and greatest causal relationship to IMP and study procedure assessed by Principal Investigator and sponsor

- All Treatment Emergent AEs leading to study discontinuation by SOC and PT

For these summaries, if a subject has repeated events of a particular TEAE, only the most severe event or the event with the strongest causal relationship to IMP will be counted in the summary tables.

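### Protocol 9.4.2 monitors unrelated SAEs to confirm there is no link to the conduit, but the plan gives only counts and percentages, which cannot support that

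*Protocol*

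**What the plan says.** Protocol 9.4.2 excludes SAEs that the investigator judges unrelated to the study conduit from expedited reporting to authorities and ethics committees. In place of that, the sponsor watches them during the study "for any difference in frequency to confirm that there is not a link to the implanted conduit". It adds: "If aggregate analysis of these events indicates they occur more frequently with the IMP, an expedited safety report may be submitted". No margin, interval, event grouping or review schedule is attached to either sentence.

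On analysis, Protocol 10.4 tests only the adjudicated access-related infection rates and then says "All other safety data will be described only (i.e., no inferential statistics". SAP 7.2 (Adverse Events Summaries) defines the overall summary, which includes treatment-emergent SAEs and deaths, by numbers, percentages and episode counts. It introduces the tables by system organ class and preferred term with "the following safety data with no inferential statistics will be provided".

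Protocol 3.2.2 and SAP 2.1 nevertheless list comparing the safety and tolerability of the two conduits as a secondary objective. SAP 6.1 justifies censoring deaths partly on the ground that "it is likely that the non-product related death rate will be similar in the two arms".

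**The concern.** Seeing no difference is not the same as showing that none exists. What separates the two is the precision of the comparison, and the plan produces nothing that shows it. A reader of the planned tables would see two percentages per row and could not tell whether similar figures rule out an important excess or merely fail to reveal one.

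This matters more than usual here because relatedness is judged at open-label sites. The comparison between arms is the check against a conduit-linked event being classed as unrelated. Death deserves particular attention: the SAP expects similar non-product mortality in the two arms, and no planned analysis estimates the mortality difference.

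**Working it through.** The documents state no power, margin or precision for SAE monitoring, so there is no figure of the plan's own to reproduce. The check asks what a 95% interval would show if the arms looked the same.

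**Inputs**
- Arm size: 175 per arm, from the Protocol Summary ("At least 350 evaluable subjects with implanted study conduits; 175 with Human Acellular Vessel (HAV), 175 with an expanded polytetrafluoroethylene (ePTFE) graft").
- Mortality: about 20% per year, from SAP 6.1.
- Follow-up: 24 months, the period in which Protocol 9.4 has all AEs reported. Complete follow-up is assumed.
- SAE incidence: not given in the documents. Values from 1% to 20% of subjects are assumed.
- Confidence level: two-sided 95%, the general convention in SAP 4.

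**Death, equal in both arms**
1. Survival at 24 months = 0.80 × 0.80 = 0.64, so 36% die.
2. Expected deaths = 0.36 × 350 = 126.
3. SE of the log hazard ratio ≈ 2/√126 = 0.178.
4. 95% limits around a hazard ratio of 1 = exp(±1.96 × 0.178) = 0.71 to 1.42.
5. With fewer observed deaths through censoring, the upper limit is exp(3.92/√100) = 1.48 at 100 deaths and exp(3.92/√80) = 1.55 at 80.

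**SAE category, equal counts x in each arm**

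SE of the log risk ratio = √[2(1/x − 1/175)]; limits = exp(±1.96 × SE).

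| Assumed incidence | x per arm | SE | 95% CI for risk ratio |
|---|---|---|---|
| 1% | 2 | 0.994 | 0.14 to 7.0 |
| 2% | 4 | 0.699 | 0.25 to 3.9 |
| 5% | 9 | 0.459 | 0.41 to 2.5 |
| 10% | 18 | 0.316 | 0.54 to 1.9 |
| 20% | 35 | 0.214 | 0.66 to 1.5 |

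At 5% or below, identical counts leave a doubling inside the interval. From about 10% a doubling is excluded, but a 1.5-fold excess is still inside at both 10% and 20%.

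**How sensitive the written watch is**

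Taken literally, the watch responds to any numerical HAV excess. The table gives the exact binomial probability that the HAV count exceeds the ePTFE count, and the probability that the lower 95% limit of the risk ratio exceeds 1 (175 per arm).

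| True ePTFE v HAV | Any excess | Lower limit above 1 |
|---|---|---|
| 2% v 4% | 83% | 10% |
| 5% v 7.5% | 80.5% | 14% |
| 5% v 10% | 96% | 41% |
| 10% v 15% | 91% | 28% |
| 20% v 30% | 98% | 58% |
| 10% v 20% | 99.5% | 74% |

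As a screen, the written watch is sensitive. What it cannot do is confirm absence.

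**Do the death-as-event analyses fill the gap?**

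Protocol 10.3.4 and SAP 6.1 and 6.3 repeat the patency analyses with death as an event. Their hazard ratio is for loss of patency or death, whichever comes first. A mortality difference can be offset or diluted by patency losses, and deaths after abandonment do not enter. These analyses address whether censoring deaths changes the efficacy result, not how mortality compares between arms.

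**The case against.** The best defence is that 9.4.2 is pharmacovigilance text and not a hypothesis test. Reporting adverse events without testing is an explicit choice, and comparing safety need not mean a p-value. No passage says that the study report will declare no link because frequencies look equal.

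There are also real safeguards. The DMC reviews safety unblinded by arm, receives interim data periodically and sees programme-wide HAV safety data. Its charter is not among the documents and may hold thresholds. The sponsor also assesses relatedness, and both assessments are tabulated (SAP 7.2). Investigators' SAE reporting duties do not depend on relatedness (Protocol 9.4.2).

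All of that stands, and it limits the point to the wording and the missing estimates. An interval is not a significance test, so the choice not to test does not explain leaving it out. The general rule in SAP 4 on 95% confidence intervals does not fill the gap: it applies unless otherwise noted, and Protocol 10.4 rules out inferential statistics for these data.

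A reader might go further and infer that relevant harms would mostly be missed, or that chance excesses would trigger reports. The documents support neither. High miss rates arise only under a 5% significance rule, which the plan does not contain for SAEs; under the literal wording an excess would usually be seen in the scenarios above. They also depend on SAE incidences that the documents do not give. A chance excess does not force a report, because 9.4.2 makes the report discretionary and rests it on an aggregate analysis.

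**Conclusion.** The point holds in this limited form: 9.4.2 states a purpose that the planned outputs cannot serve, and the safety comparison objective is left without any estimate of precision for SAEs or death. Under the most favourable case of exactly equal deaths, the data would still be compatible with a hazard ratio of about 1.4. That figure rests on about 20% annual mortality, 24 months and complete follow-up; with 80 to 100 observed deaths the limit is about 1.5. For SAEs at 5% or less, equal counts do not exclude a doubling; this rests on assumed incidences.

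The point does not show that the monitoring is insensitive, that the trial will wrongly declare safety, or that the primary patency analysis is affected. The wording change alone would be minor; the missing interval estimates make it worth acting on.

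**What to change.** 1. In Protocol 9.4.2, replace the purpose of confirming that there is no link with: *to look for a between-arm difference*.
2. In SAP 7.2 (Adverse Events Summaries), add HAV:ePTFE estimates with two-sided 95% confidence intervals up to Month 24 for all-cause death (hazard ratio), and for all SAEs and non-conduit-related SAEs (exposure-adjusted first-event rate ratios). Label them as estimation, with no significance claim, and amend Protocol 10.4 to allow them. Month 24 is the natural limit because Protocol 9.4 afterwards restricts reporting to HAV-related SAEs and Events of Special Interest.
3. Give the same table to the DMC.

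Do not replace the any-difference watch with a trigger that requires the lower limit to exceed 1. For 5% v 10% that would cut the chance of a signal from 96% to about 41%, and for 2% v 4% from 83% to about 10%.

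The cost is small text changes and a few tables from data already collected, with no new patients and no effect on the primary analysis. The downside is that the intervals will be wide and unadjusted for multiplicity, and the safety statement will be less favourable, for example that an excess in deaths of around 40% was not excluded.
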